1.1 Background and Significance

Female sexual health is an important determinant in quality of life, contributing to both increased meaning in life and general well-being [1]. Unfortunately, approximately 41% of women suffer from female sexual dysfunction (FSD) [2]. There are several domains that contribute to sexual dysfunction. Difficulty with genital arousal can arise from low activity in the nerves or blood vessels of the genitals. Problems with low sexual interest can stem from hyperactivity in the brain. Some women suffer from FSD due to neurological conditions such as spinal cord injury (SCI). After injury, neural connections between central sexual function neural circuits (e.g. desire) and peripheral sexual functions (e.g. genital arousal) are interrupted. Although not a factor in mortality, sexual function remains a critical component of quality of life after SCI and is frequently reported as a high priority for restoration [3], [4].

A challenge in studying sexual function in women is the complexity of sexual arousal, which includes both cognitive desire and genital arousal components [5]. Overall female sexual function is not well understood, which contributes to the lack of good treatment options for dysfunction, regardless of type. Pharmaceuticals such as sildenafil (viagra) have occasionally been reported to improve genital arousal [6] but results are inconsistent and frequently present with mild to moderate side-effects [7]. There is a need for an effective treatment for women who have genital arousal deficiencies without concurrent side-effects. The ultimate goal of this research is to provide improvement in genital sexual arousal for women FSD due to either neurogenic (i.e. SCI) or non-neurogenic causes.

One treatment avenue is the use of electrical stimulation on targeted nervous system pathways. Sacral neuromodulation (SNM) and percutaneous tibial nerve stimulation (PTNS) are common third-line treatments for irregularities in pelvic organ function, such as bladder incontinence, and have been used for decades [8]. Some patients undergoing SNM or PTNS to improve bladder function have also reported an improvement in their sexual health as an additional benefit [9]. This is not entirely unexpected, as organs of the pelvic floor share common nerve pathways and spinal circuits [10]. For example, the sacral root targeted by SNM gives rise to the pudendal nerve, of which a distal branch is the genital nerve. Each has been a target for electrical stimulation to treat bladder problems and may also be a treatment option for FSD. This neuro-functional overlap gives reason to believe that the nerves that innervate the organs associated with genital arousal and that have been previously targeted in bladder neuromodulatory studies are a viable treatment option for women with genital arousal deficiencies.

In order to explore the potential for electrical stimulation to modulate genital arousal, our lab has started a research focus of examining peripheral nerve stimulation to address female sexual dysfunction, targeting pudendal and tibial nerve pathways [11]–[14]. In animal studies we have shown that tibial and genital nerve stimulation can lead to increases in vaginal blood flow [11], [12], which is an indicator of sexual arousal [15]. A human subjects study from our group (HUM00101713) focused on non-neurogenic subjects with FSD and showed that stimulating the posterior tibial and dorsal genital nerves repeatedly across twelve weekly sessions are feasible approaches for improving sexual function based on improvements in clinically validated surveys [13]. The mechanisms that underlie this clinical effect, such as whether the applied nerve stimulation increases vaginal blood flow in women, are still largely unknown. This study aims to address this gap, to study the short-term effect of stimulation on vaginal blood flow. To potentially amplify any stimulation effects, this study will incorporate the use of sexually explicit films, a method that is standard in sexual function studies [16]–[18]. The inclusion of healthy

women and non-neurogenic women with FSD will also provide information about the underlying neural circuitry, based on whether either stimulation approach has better efficacy in spinal intact or damaged participants. While genital nerve stimulation is generally successful at improving bladder function in individuals with SCI, tibial nerve stimulation has had mixed results. These findings by other researchers suggest potential outcomes for our different study groups.

1.2 Objective

The overall purpose of this research is to improve sexual function in women with sexual dysfunction. The goal of this study is to see if either of two nerve stimulation interventions cause a short-term change in vaginal blood flow. The effect of this intervention will be compared between women who have neurogenic (spinal cord injury) or non-neurogenic dysfunction and healthy women, to reveal mechanisms underlying neural control over vaginal blood flow.

1.3 Specific Aims

The aims of this study are to:

- Aim 1: Compare the effect of skin-surface genital nerve stimulation and tibial nerve stimulation on vaginal blood flow in women with spinal cord injury caused neurogenic sexual dysfunction.
- Aim 2: Compare the effect of skin-surface genital nerve stimulation and tibial nerve stimulation on vaginal blood flow in women with non-neurogenic female sexual dysfunction.
- Aim 3: Compare the effect of skin-surface genital nerve stimulation and tibial nerve stimulation on vaginal blood flow in neurologically-intact women without sexual dysfunction.

1.4 Primary Outcomes

The primary outcome measure in this study is the maximum change in VPA from the average baseline value for each stimulation location across each stimulation participant group. To determine if participant type, stimulation location, and stimulation interval (i.e. timing within stimulation duration) has an effect on VPA, an ANOVA will be performed.

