As shown in Figure 4, during the testing period participants will first view a 5-minute neutral film depicting nature scenes to allow blood flow levels to stabilize. This will be followed by a 10-minute period while the subject watches an erotic film clip for assessment of arousal responses without electrical stimulation. The erotic film clip depicts sexually explicit material of two consenting adults engaging in sexual activities including manual and oral stimulation of breasts and genitals as well as penile-vaginal intercourse depending on the film chosen. A 10-minute clip of the same neutral film will follow, to allow blood flow levels to return to baseline. Five minutes into this film, electrical stimulation will be resumed at the previously determined amplitude. Finally, the subject will view another 10-minute erotic film clip depicting similar sexually explicit material as the first while electrical stimulation remains on as the last sequence in the testing.

At the beginning of the VPA recording sequence, in between each video transition, and at the end of the VPA recording sequence (a total of 5 times), participants will view a 15-30-second screen prompt asking them to record their agreement with the statement, “I feel sexually aroused (e.g. sexually excited, turned on) right now,” according to a 5-point Likert scale: (1) *strongly disagree*, (2) *disagree*, (3) *neutral*, (4) *agree*, and (5) *strongly agree*. At the end of each session participants will be asked their general opinions of that stimulation session, whether it seemed to elicit any genital arousal responses such as lubrication, warmth, tingling, or any

sensations they would characterize as pleasurable, and whether they would consider further use of it.

At the second study day, stimulation using the same steps will be performed at the other location.

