3.2 Data Analysis plan

VPA will undergo optimization, filtration, and a spectral analysis as in [11], [12], [15]. The change in VPA from the average baseline value will be determined for each stimulation at four-minute intervals, during which stimulation is paused for ten seconds. Although VPA will be recorded continuously, the genital nerve stimulation may cause a motion artifact and so equal pauses in stimuli will be used in each interval for both stimulation approaches. We may eliminate this pause if data analysis indicates that there are no artifacts or that filtration and spectral analysis eliminates artifacts. Similar calculations may be done for the heart rate and blood pressure. An ANOVA will be performed to determine whether participant type, stimulation location, and stimulation interval (i.e. timing within stimulation duration) has an effect on VPA. Wilcoxon signed rank tests will be used to test for differences within the groups. Similarly, changes in cardiovascular parameters will be assessed, to see if general autonomic responses are triggered with either stimulation location or patient group. We will also look for correlations between the pre-session survey scores (e.g. FSFI total score), patient demographics (e.g. age,

BMI), and changes in items (e.g. decrease in incontinence events) with the maximal VPA responses with a regression analysis.

4. Study Recruitment

This study addresses a potentially sensitive topic. During the recruitment and consenting processes, all study activities will be carefully explained with particular attention to matters of privacy and confidentiality. Many women with spinal cord injury (SCI) have had negative healthcare experiences with respect to reproductive health. Alternatively, grateful patients can feel compelled to participate out of a sense of loyalty. As such, for recruitment and consenting processes, we will emphasize that participation is entirely voluntary, and refusal or withdrawal will have no effect on any care they receive.

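### Baseline VPA enters only by subtraction; adjusting for it within women could sharpen the genital-versus-tibial contrast at little cost, but the gain is unknown

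*Combined protocol and SAP*

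**What the plan says.** Section 1.4 defines the primary outcome as a change score: "The primary outcome measure in this study is the maximum change in VPA from the average baseline value for each stimulation location". Section 3.2 applies the same subtraction within the session: "The change in VPA from the average baseline value will be determined for each stimulation at four-minute intervals".

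The model terms are in the same section: "An ANOVA will be performed to determine whether participant type, stimulation location, and stimulation interval". No baseline VPA, woman or period term is listed. Comparisons inside a participant group go to a rank test: "Wilcoxon signed rank tests will be used to test for differences within the groups". The only regression planned is exploratory: "We will also look for correlations between the pre-session survey scores (e.g. FSFI total score), patient demographics (e.g. age". It goes on to BMI and to changes in items, and does not list baseline VPA.

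Under 2.2, each woman attends twice, one to five months apart. One location is randomly selected for the first visit and the other is used at the second, so each location has its own session baseline. The data for a covariate exist, since 3.2 notes: "Although VPA will be recorded continuously". Two stretches of neutral film precede stimulation. The first opens the session: "participants will first view a 5-minute neutral film depicting nature scenes to allow blood flow levels to stabilize". The second comes after the first erotic clip: "A 10-minute clip of the same neutral film will follow, to allow blood flow levels to return to baseline"; stimulation starts five minutes into it. Neither 1.4 nor 3.2 says which stretch supplies the average baseline.

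**The concern.** Each of Aims 1 to 3 is a comparison of genital with tibial stimulation inside one participant group, and the groups hold 10, 10 and 20 women. The comparison is made between two sessions at least a month apart, with the sensor placed anew each time. The planned contrast is the between-session difference in stimulated VPA minus the between-session difference in baseline VPA, so the baseline difference carries a fixed weight of 1.

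That weight is optimal only if a one-unit baseline difference between a woman's sessions predicts a one-unit difference in her stimulated VPA. If it predicts less, subtraction over-corrects; if more, it under-corrects. Either way, baseline variation that could have been removed stays in the contrast and widens its interval. With groups this small, a chance baseline imbalance between the two locations need not average out. A covariate that estimates the slope would remove this, and it needs no new measurement.

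**Working it through.** **The plan's own figure.** 3.1 gives 10 + 10 + 20 = 40, which agrees. There is no power calculation, SD or correlation to reproduce.

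**Inputs.** From the documents: groups of 20, 10 and 10 (3.1), and one session per location per woman (2.2). Assumed, because the documents give no value: rho from 0.2 to 0.9 and k of 1, 1.5 and 2. Here dY and dB are a woman's genital-minus-tibial differences in stimulated and baseline VPA, rho is their correlation, and k = SD(dY)/SD(dB).

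**Formulas, per woman, in units of SD(dB) squared.**
- Change score, dY − dB: k² + 1 − 2·rho·k.
- Adjusted for dB: k²(1 − rho²).
- Ratio: R = 1 + (1 − rho·k)² / [k²(1 − rho²)].

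R equals 1 only when the slope rho·k equals 1. At k = 1 it reduces to 2/(1 + rho).

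**Cost of estimating the slope.** With one slope common to three groups, dB has 40 − 3 = 37 within-group degrees of freedom. Under normality the variance of an adjusted group contrast rises by a factor of 1 + 1/35 = 36/35 = 1.029. The ratio in use is R/1.029, and its floor is 1/1.029 = 0.97.

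**Worked example, rho = 0.5.**
- k = 1: R = 1 + 0.25/0.75 = 1.333; divided by 1.029, 1.30.
- k = 1.5: R = 1 + 0.0625/1.6875 = 1.037; divided by 1.029, 1.01.
- k = 2: the slope is exactly 1, so R = 1; divided by 1.029, 0.97.

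**Variance of change score relative to adjusted, group of 10, common slope.** Each cell gives the formula, then simulation.

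| k | rho 0.2 | rho 0.5 | rho 0.7 | rho 0.9 |
|---|---|---|---|---|
| 1 | 1.62; 1.64 | 1.30; 1.28 | 1.14; 1.14 | 1.02; 1.02 |
| 1.5 | 1.19; 1.20 | 1.01; 1.01 | 0.97; 0.97 | 1.25; 1.25 |
| 2 | 1.06; 1.06 | 0.97; 0.97 | 1.05; 1.05 | 1.79; 1.81 |

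The two agree within 0.02. A period term would use one more degree of freedom (1 + 1/34 = 1.029), which leaves the table essentially unchanged.

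**Separate slopes.** Estimating the slope inside one group of 10 costs (10 − 2)/(10 − 3) = 1.143. At k = 1 the break-even is 2/(1 + rho) = 1.143, or rho = 0.75; above that, adjustment loses slightly.

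**Validity and power.** In simulations of the paired contrast with 10, 20 or 40 women (two-sided 5%), type I error was about 5% for both analyses. With 40 women, rho = 0.5 and an effect of 0.45 SD of dY, power was 79% for change score and 89% adjusted at k = 1, but 88% and 89% at k = 1.5.

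**The maximum as endpoint.** These formulas treat the response as a mean. Taking the maximum of four noisy intervals (assumed noise SD 0.5, equal SDs before noise) gave 1.55, 1.24, 1.12 and 1.00 across the four values of rho, so the pattern holds but the figures are indicative.

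**The case against.** Change from baseline is a valid analysis and matches the stated goal in 1.2, a short-term change in blood flow. Subtraction also does useful work. An additive shift shared by baseline and response, such as one caused by re-placing the sensor, is removed completely; only the unshared part is added noise. This is a declared pilot with no power analysis, and the size of any gain depends on two unknown quantities. All of this stands, and it is why the point is optional.

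A reader might infer a stronger case in three ways, none of which the documents support.
- That baseline differences bias the site comparison. The first location is randomly selected, so there is no unconditional bias, and simulated type I error is near 5%. What remains is conditional: given an observed baseline imbalance, the change-score contrast is shifted by (slope − 1) times that imbalance.
- That any correlation below 1 makes the higher-baseline session show the smaller change. The criterion is the slope, rho·k. At rho 0.5 and k = 2, subtraction is optimal; above a slope of 1 the direction reverses.
- That a definite gain can be quoted, for example that 10 adjusted women are worth about 13 at rho 0.5 (10 × 1.28 = 12.8). That requires k = 1. At k = 1.5 the figure is about 10.1, and at k = 2 about 9.7. Since the baseline is an average and the outcome a maximum under stimulation and erotic film, k above 1 is plausible.

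It is also fair to object that a common slope is an assumption in a study asking whether neural control differs between groups, and that the Wilcoxon tests cannot carry a covariate. The fix has to deal with both.

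**Conclusion.** The point holds as one of precision. Sections 1.4 and 3.2 fix the within-woman slope at 1 in the genital-versus-tibial contrast, although the data to estimate it are recorded. Over the settings tabulated, adjustment with a common slope costs at most about 3% in variance. Against that, the change-score contrast may be no noisier than the adjusted one or may have up to about 80% more variance.

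Where the trial lies in that range cannot be told from the documents. The figures assume normal, mean-type responses, complete pairs, one slope shared by the three groups, and the stated values of rho and k. The uneven balance of small cost against possible gain favours adjustment, but the planned analysis is not invalid without it. It is a change to consider.

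**What to change.** In 1.4 and 3.2:

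1. State which pre-stimulation neutral-film window is the baseline, and use the same window in both sessions. The covariate cannot be specified until this is done.
2. Analyse the change (or the stimulated level) in a model with woman and period terms, alongside the planned factors. Add the session's baseline VPA minus the woman's own two-session mean as a covariate with one common slope. Centring confines the adjustment to the randomised within-woman comparison. With complete pairs the site contrast is the same for either outcome; keeping the change also leaves the comparison of the non-randomised participant types as planned.
3. Take the within-group site contrasts for Aims 1 to 3 from this model, and keep the Wilcoxon signed rank tests on change scores as a sensitivity analysis.

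The cost is SAP wording and one degree of freedom for the covariate; the period term takes another. No new data or visits are needed. The downsides are the assumption of a common slope across groups and a precision loss of about 3% if the true slope is near 1.

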electrodes (ValuTrode Fabric CF3200 or equivalent) will be placed on either lateral side of the clitoris (Figure 1). For tibial nerve stimulation, the two electrodes will be placed just above the medial malleolus and the ipsilateral calcaneus on one leg (Figure 2). The placement of TENS device will be performed by clinical study team members, specifically [name], [name], or other clinical practitioners or fellows who are study team members. Each clinical study team member is a practicing MD physician trained in the use of neuromodulation including technology such as this. The conductivity of the electrodes may be tested with an impedance meter (Digitimer D175), which is connected to an electrode set and uses very low, imperceptible current levels. If the meter indicates poor conductivity, the electrodes may be repositioned.

[figure not shown]

Figure 2. Electrode locations (white circles) for tibial nerve stimulation near the ankle.

Prior to starting stimulation with a TENS device (Empi Select, or similar), the stimulation amplitude will be determined. The current will be increased until the participant expresses discomfort and then reduced to a comfortable level, or a maximum level of 60 mA is reached. During stimulation, the set stimulation amplitude will be applied at a frequency of 20 Hz, which is standard for PTNS and the frequency we used in our previous human subjects' study (HUM00101713).

Participants will be shown a neutral video (nature film excerpt) and an erotic film clip featuring sexually explicit material at different intervals of the testing period. The use of videos in this manner is a standard method in studies of sexual function [16]–[18], and may help enhance an arousal response. Two videos will be loaded on a laptop computer in a fixed order that will not require patient intervention. Participants will choose a video based on their preference in viewing either two women or a woman and a man engaging in sexual activities.

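### The primary outcome, a maximum VPA change from baseline, is not the quantity the planned ANOVA can use, is positive on average with no response, and mixes film with stimulation

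*Combined protocol and SAP*

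**What the plan says.** Section 1.2 states the question: "The goal of this study is to see if either of two nerve stimulation interventions cause a short-term change in vaginal blood flow". It also asks for a comparison between participant groups. Each aim in section 1.3 is narrower: "Compare the effect of skin-surface genital nerve stimulation and tibial nerve stimulation on vaginal blood flow" within one group.

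Section 1.4 defines the primary outcome as "the maximum change in VPA from the average baseline value for each stimulation location", across participant groups. Its next sentence plans an analysis with participant type, location and interval as factors: "stimulation interval (i.e. timing within stimulation duration) has an effect on VPA, an ANOVA will be performed".

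Section 3.2 derives a change from average baseline at four-minute intervals and repeats that ANOVA with VPA as the response. It adds Wilcoxon signed rank tests within groups without naming the variable or the pair. It mentions maximal VPA responses once, in a regression on survey scores, demographics and changes in other items.

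Section 2.2 gives the session order: 5 minutes of neutral film; 10 minutes in which the participant "watches an erotic film clip for assessment of arousal responses without electrical stimulation"; 10 minutes of neutral film; then "another 10-minute erotic film clip depicting similar sexually explicit material as the first while electrical stimulation remains on". On the second neutral film it says: "Five minutes into this film, electrical stimulation will be resumed at the previously determined amplitude". It says of the videos that their use is standard "and may help enhance an arousal response".

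**The concern.** There are three linked problems.

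1. **Outcome and analysis do not match.** Each location is tested on one visit, so the natural reading is one maximum per session. A single maximum has no interval level, so the ANOVA must run on the per-interval changes. A reader cannot tell which quantity is primary.
2. **A maximum is not centred at zero.** The largest of several noisy values minus an average tends to be positive when nothing happens. This bears on the section 1.2 question, and on any comparison of locations or groups whose recordings differ in noise.
3. **Film and stimulation are mixed.** Most of the stimulated time is erotic film, so a change from baseline contains the film response. The plan records the comparator that would separate the two and does not use it.

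At stake is whether a reported rise can be attributed to stimulation, and whether the choice between maximum and interval values stays open until the data are seen.

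**Working it through.** **Inputs from the documents.** Groups of 10, 10 and 20 (section 3.1). Four-minute intervals (3.2). Stimulated time by section 2.2: 5 min neutral + 10 min erotic = 15 min, and 15/4 = 3.75, so 3 complete intervals or 4 if the last is partial. Section 15.4 gives 20 min, and 20/4 = 5. The plan states no SD, correlation, alpha or effect size, so it has no figure of its own to reproduce.

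**Assumptions.** Normal noise with SD 1 per interval value; correlation rho between intervals; one baseline error per session with SD b; no drift; two-sided 0.05. The middle case is 3 windows, rho = 0.5, b = 0.5.

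**1. Structure.** One maximum per woman and location gives 2 values per woman. An ANOVA with an interval factor needs 2 locations × 3 to 5 intervals = 6 to 10 values per woman.

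**2. Mean of the maximum with no response** = E(max of k standard normals) × √(1 − rho), in SD of interval noise:

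| Windows k | rho 0 | rho 0.5 | rho 0.8 |
|---|---|---|---|
| 3 | 0.85 | 0.60 | 0.38 |
| 4 | 1.03 | 0.73 | 0.46 |
| 5 | 1.16 | 0.82 | 0.52 |

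With 3 or 4 windows and b from 0 to 1, 61% to 94% of individual maxima exceed zero.

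**3. Genital versus tibial on the maximum.** With equal noise and equal k the two means cancel: bias 0, and the paired signed-rank test rejects in about 5% of simulated trials. If genital noise SD were 1.25 times tibial (assumed), the bias is 0.25 × the tabulated value, from 0.25 × 0.38 = 0.09 to 0.25 × 1.03 = 0.26 SD. A group with 1.5 times the within-session SD would show a false excess of 0.5 × 0.846 = 0.42 SD (k = 3, rho 0).

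**4. The maximum tested against zero** (not specified in the plan). Simulated rejection with no response in the middle case: 37% at n = 10 and 68% at n = 20.

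**5. Film.** By section 2.2, 10 of 15 stimulated minutes are erotic. Reading values at 4, 8 and 12 min of stimulation puts the first in neutral film and two in erotic film. Suppose the film alone adds 0.5 SD (assumed). The mean change from baseline then shifts by 0.5 × 2/3 = 0.33 SD, against an SD of √(0.5 + 0.5/3 + 0.25) = 0.96. With no stimulation effect, a test of that mean against zero rejects 16% (n = 10) and 30% (n = 20). Replacing the maximum by a mean is therefore not enough. In stimulated minus matching unstimulated windows of the same session, film effect and baseline error both cancel, and rejection is 4.5% to 5.3% if there is no order effect.

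**6. Precision of the location difference** (middle case, independent sessions; Var(max of 3) = 0.56):

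- Planned maximum: √[2 × (0.5 + 0.5 × 0.56 + 0.25)] = 1.43
- Mean change from baseline: √[2 × (0.5 + 0.5/3 + 0.25)] = 1.35
- Matched contrast, 3 windows, shared noise lasting the whole session: √[2 × 2 × 0.5/3] = 0.82
- Matched contrast, 3 windows, shared noise separate in the two blocks: √[2 × 2 × (0.5 + 0.5/3)] = 1.63
- Matched contrast on the two erotic windows only, by the same formulas with 2 in place of 3: 1.00 and 1.73

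**The case against.** The strongest reply is that the plan never tests the maximum against zero. Both locations are tested in every woman and Aims 1-3 are location comparisons within a group, so the natural Wilcoxon pair is genital versus tibial. On that reading the upward bias cancels when noise is equal, which the equal stimulation pauses are meant to support. This stands. A reader might infer from the 37% and 68% above that the planned test has that error rate. The documents do not support it, because those figures need a test that section 3.2 does not specify. Equal noise is intended but not assured: section 3.2 expects possible motion artifact with genital stimulation and allows the pauses to be dropped.

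Nor can it be said that the maximum has no analysis, since section 3.2 assigns it a regression. That regression is correlational and tests no effect of stimulation, location or group.

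It would also be too strong to say that the baseline is wholly undefined. Section 2.2 says that neutral film lets blood flow stabilise and return to baseline, and Figure 4, not shown in the text available, may mark the period. A neutral-film baseline would still leave the film response inside the outcome.

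If the maximum were taken within each four-minute interval it could enter the ANOVA, but the upward bias would remain. Downward drift of VPA could offset the bias. Pilot status explains the missing power calculation but not an unclear primary quantity.

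**Conclusion.** The point holds and should be fixed. Two parts follow from the text alone: the named primary outcome is not what the ANOVA analyses, and a change from baseline cannot separate stimulation from film, although the unstimulated film is recorded in every session. The upward bias of the maximum is certain in sign if VPA varies within a session and does not drift down. Its size, +0.38 to +1.03 SD for 3 or 4 windows, rests on assumed correlations and normal noise. The exposure is to the section 1.2 question and to comparisons between locations or groups with unequal noise. The paired comparison in Aims 1-3 is not invalid under equal noise.

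**What to change.** In sections 1.4 and 3.2:

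- Name one primary quantity. For each woman and location: mean VPA over pre-specified stimulated erotic-film windows minus mean VPA over the matching unstimulated erotic-film windows of the same session.
- For Aims 1-3, test the within-group genital-versus-tibial difference in that quantity with the Wilcoxon signed rank test.
- For section 1.2, report the within-session contrast itself, with the caveat that unstimulated film always comes first.
- Analyse the per-interval values in a repeated-measures model with group, location and interval, and participant as a random effect.
- Keep the maximum as a descriptive secondary, compared only with a maximum over the same number and length of unstimulated windows.
- Treat the neutral-film contrast as supportive. Its two periods are not matched: one opens the session and the other follows an erotic film.
- Reconcile section 2.2 (15 minutes implied) with section 15.4 (20 minutes), because they set the number of windows.

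**Cost.** Wording only; the data are already collected. A mean dilutes a brief peak: a response in one of three windows counts a third. The within-session contrast carries any order effect. An assumed 0.25 SD gives 9% to 23% rejection at n = 10 and 14% to 44% at n = 20 (rho 0.5, three windows). The location comparison does not carry it if it is equal in both sessions. Precision may improve or worsen against the planned maximum, depending on how long shared noise lasts (step 6 of the working).
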